9.1 Study Design

The study will be conducted as a collaborative study involving five research centers: one coordinating center, RTI Health Solutions in Spain and the United States, and four database research partners—the PHARMO Institute for Drug Outcomes Research in the Netherlands, Southern Denmark University in Denmark, the Karolinska Institutet in Sweden, and the Clinical Practice Research Datalink (CPRD) in the UK. Each participating database research partner will adapt this core protocol to the specific needs of the local database.

The coordinating center will have the following primary roles and responsibilities:

- Serve as the coordinating center for the study
- Lead preparation of the final version of this core study protocol with input from all research partners
- Guide database-specific adaptation of the protocol, with a focus on consistency with the core protocol of variable definitions and other methodological aspects across adapted protocols
- Provide scientific support to the study implementation phase, including case validation efforts
- Support integration of study results by analyzing stratified data from each database research partner to estimate overall measures of effect
- Facilitate research network communications, study reporting, and dissemination of study results

The database research partners will have the following primary roles and responsibilities:

- Provide input into the development of this core protocol
- Develop the protocol adaptation to each database
- Implement the study in the respective database
- Liaise with the coordinating center during study implementation as needed
- Contribute to the preparation of study reports and dissemination of results

The sponsor will have the following primary roles and responsibilities:

- Provide funding for the study
- Provide input into the development of this core protocol
- Review and provide input during the study implementation phase

The study will be conducted in two phases:

- Phase I. Completed on December 11, 2015. The study included the period from the date of first availability of topical tacrolimus and topical pimecrolimus in each study population through December 31, 2011.

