9.3.5 Endpoints

Incident malignancies are defined as the first occurrence of one of the malignancies of interest occurring in study patients during study follow-up. If a person develops more than one primary malignancy of interest (i.e., a malignant melanoma and a lymphoma), only the first malignancy will be included and counted as an individual record. In a sensitivity analysis, the occurrence of each endpoint will be evaluated regardless of a prior occurrence of any of the other study endpoints during the study period.

The third version of the International Classification of Diseases for Oncology (ICD-O-3), which provides site (topography) and histology (morphology) codes for neoplasms, will be used to define malignancies in the study. The ICD-O-3 topography code C44 (skin) will be used together with the corresponding morphology codes to identify malignant melanomas (MM) and non-melanoma skin cancers (NMSC). The complete lists of ICD-O-3 codes for the malignancies of interest are presented in Annex 4.

The following incident malignancies will be included in the study.

Skin Malignancies

- Malignant melanoma, including in situ carcinomas (MM)
- Non-melanoma skin cancer (NMSC), including in situ carcinomas (i.e., squamous cell and basal cell carcinomas, Merkel cell carcinoma, and adnexal and skin appendages neoplasms)

Skin malignancies will be evaluated as a group (“Any skin malignancy”) and by individual malignancy type—i.e., melanoma, NMSC. In a sensitivity analysis, NMSC will be further subclassified as basal cell carcinoma and squamous cell carcinoma.

Lymphomas

- Cutaneous T-cell lymphomas (CTCL)
- Hodgkin lymphomas (HL)
- Non-Hodgkin lymphomas (excluding CTCL)

Lymphomas will be analyzed as a group (“Any lymphoma”) and by specific lymphoma type—cutaneous T-cell lymphoma, Hodgkin lymphoma, and non-Hodgkin lymphoma (excluding CTCL). In a sensitivity analysis, lymphomas will be grouped as cutaneous or noncutaneous lymphomas.

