selected the ICD-O-3 codes that matched the definition and codes of cutaneous lymphomas in the WHO 2008 classification (see Annex 4, Table A4-3). This approach did not pose any problem for the identification of CTCLs. However, the identification of CBCLs (classified as a separate entity in WHO 2008) was not possible as the WHO 2008 codes for these tumors do not have correspondence in ICD-O-3. Therefore CBCLs (which occur considerably less frequently than CTCLs) will not be included within the cutaneous lymphomas group in this study although they are still expected to be identified as non-Hodgkin lymphomas in the study databases and would count toward that endpoint. Moreover, certain other rare lymphomas that were newly included with provisional codes in the WHO 2008 classification (and which are proposed for inclusion in the next edition of ICD-O), for example, primary cutaneous gamma-delta T-cell lymphoma, will not be explicitly included in this study. However, such lymphomas, if any occur in the study population and are coded less specifically, would be included in the non-Hodgkin lymphoma endpoint.

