9.3.6 Case Identification and Validation

Potential cases of the targeted malignancies will be identified in PHARMO, Denmark, and Sweden using the list of ICD-O-3 codes shown in Annex 4. The development of a case validation approach will depend on whether validation of cases of neoplasms had been performed as part of the standard validation procedures by the data source from which cases originate (e.g., cancer registries, pathology registries, electronic medical records). Cases that are identified and recorded in the cancer registries will not require further validation because of the standard validation procedures used by the cancer registries

In, Denmark, and Sweden, cases will be identified through cancer registries and will not require validation [15].

In PHARMO, as in Phase I, cases will be identified in the pathology database (PALGA), which is mapped to the ICD-O-3 classification. Cases identified will be validated by an independent pathologist by reviewing the pathology excerpts of all pediatric cases, a random sample of adult cases, and all cases of CTCL. Staging information is not directly available in PALGA. In order to conduct the sensitivity analysis to assess surveillance bias (Section 9.7.2.5), staging information will be obtained from the Netherlands Cancer Registry (NCR). The sensitivity analysis will include all malignant melanoma cases identified in PALGA for which data from the NCR are available. Data from the NCR are currently available through 2014 and might be available through 2015 in 2018.

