In the CPRD, for practices linked to the cancer registry, cases will be identified using ICD-10 codes. For practices not linked to the cancer registry, cases will be identified through the CPRD records and linkage to Hospital Episode Statistics (HES) data. The linkage of CPRD data to cancer registry data will be performed in the study. Note that the linkage is partial, and there is a lag of 2 years for obtaining data from the cancer registry. Cases from linked practices for which cancer registry information is not available will be identified through CPRD records and HES, as for practices not linked to the cancer registry. The ICD-O-3 coding system is not used for coding neoplasms in the CPRD. Therefore, the standard reference medical terminology or diagnostic coding systems used in the database (Read/OXMIS) will be mapped to the ICD-O-3 topography and morphology codes for each endpoint. CTCLs will be identified using the selected ICD-O-3 codes that matched the definition and codes of cutaneous lymphomas in the WHO 2008 classification of lymphomas as described in Section 9.3.5. For cases identified

through the CPRD or the Hospital Episodes Statistics linkage, validation of all pediatric cases, a random sample of adult cases of melanoma skin cancers and lymphomas (number of cases to be determined based on the final number of cases identified), and all cases of non-melanoma skin cancer and CTCL will be performed by reviewing the computerized information.

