Cancer Type by Age Group	Incidence per 100,000 Person-years ^a	Probability That Upper Limit of the 95% CI of the Rate Ratio is Below			
		2	4	8	16
Age < 18 years					
Skin, non-melanoma	0.5	0.05	0.09	0.15	0.23
Melanoma of skin	1.0	0.06	0.14	0.25	0.40
Lymphoma	2.1	0.09	0.24	0.46	0.70
Non-Hodgkin lymphoma	0.5	0.05	0.09	0.15	0.23
Hodgkin lymphoma	1.6	0.08	0.19	0.37	0.58
CTCL ^b	0.2	0.04	0.06	0.08	0.11
Age ≥ 18 years					
Skin, non-melanoma	286.2	1.00	1.00	1.00	1.00
Melanoma of skin	34.7	1.00	1.00	1.00	1.00
Lymphoma	25.6	0.99	1.00	1.00	1.00
Non-Hodgkin lymphoma	18.1	0.95	1.00	1.00	1.00
Hodgkin lymphoma	4.4	0.43	0.95	1.00	1.00
CTCL	3.1	0.33	0.85	0.99	1.00

CI = confidence interval; CTCL = cutaneous T cell lymphoma.

Note: Based on a 4-year extension (additional 3-year period of inclusion plus 1 year of follow-up) accounting for 6-month induction period.

^a Incidence rates based on results from Phase I.

^b Calculations could not be based on Phase I results because there were no cases of CTCL in children unexposed to topical tacrolimus. Incidence rates are from the age- and sex-specific incidences rates from the Surveillance, Epidemiology, and End Results (SEER) program of the National Cancer Institute in the United States (SEER*Stat version 7.05).

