Bronchial-associated lymphoid tissue (BALT) lymphoma	"
BALT lymphoma	"
Skin-associated lymphoid tissue (SALT) lymphoma	"
SALT lymphoma	"
Monocytoid B-cell lymphoma	"
Nodal marginal zone lymphoma	"
MATURE T AND NK-CELL LYMPHOMAS	M970-971
Mature T-cell lymphoma, NOS	M 9702/3
Peripheral T-cell lymphoma, NOS	"
T-cell lymphoma, NOS	"
Peripheral T-cell lymphoma, pleomorphic small cell	"
Peripheral T-cell lymphoma, pleomorphic medium and large cell	"
Peripheral T-cell lymphoma, large cell	"

Cancer Description	ICD-O-3 codes
T-zone lymphoma	"
Lymphoepithelioid lymphoma	"
Lennert lymphoma	"
Hepatosplenic γ/δ (gamma-delta) cell lymphoma	M 9716/3
Intestinal T-cell lymphoma	M 9717/3
Enteropathy type intestinal T-cell lymphoma	"
Enteropathy associated T-cell lymphoma	"
PRECURSOR CELL LYMPHOBLASTIC LYMPHOMA	972
Precursor cell lymphoblastic lymphoma, NOS	M 9727/3
Malignant lymphoma, lymphoblastic, NOS	"
Malignant lymphoma, convoluted cell	"
Lymphoblastoma	"
Precursor B-cell lymphoblastic lymphoma	M 9728/3
Precursor T-cell lymphoblastic lymphoma	M 9729/3
MALIGNANT LYMPHOMAS, NOS OR DIFFUSE	M959
Malignant lymphoma, NOS	M 9590/3
Lymphoma, NOS	"
Microglioma	"
Malignant lymphoma, non-Hodgkin, NOS	M 9591/3
Non-Hodgkin lymphoma, NOS	"
B-cell lymphoma, NOS	"
Malignant lymphoma, noncleaved cell, NOS	"
Malignant lymphoma diffuse, NOS	"
Malignant lymphoma, lymphocytic, intermediate differentiation, nodular	"
Malignant lymphoma, small cell, noncleaved, diffuse	"
Malignant lymphoma, undifferentiated cell, non-Burkitt	"
Malignant lymphoma, undifferentiated cell type, NOS	"
Lymphosarcoma, NOS	"
Lymphosarcoma, diffuse	"
Reticulum cell sarcoma, NOS	"
Reticulum cell sarcoma, diffuse	"
Reticulosarcoma, NOS	"
Reticulosarcoma, diffuse	"
Malignant lymphoma, small cleaved cell, diffuse	"
Malignant lymphoma, lymphocytic, poorly differentiated, diffuse	"
Malignant lymphoma, small cleaved cell, NOS	"
Malignant lymphoma, cleaved cell, NOS	"

Cancer Description	ICD-O-3 codes
Composite Hodgkin and non-Hodgkin lymphoma	M 9596/3

NOS = not otherwise specified.

Source: International Classification of Diseases for Oncology- Third Edition (ICD-O-3)

Note: All the cutaneous lymphomas listed in Table A4-3 will also be counted toward the "non-Hodgkin lymphoma" endpoint and toward the "Any lymphoma" endpoint but for simplicity purposes the diagnoses listed in Table A4-4 are limited to those that have not already been listed in Table A4-3.

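### Section 9.3.5 excludes CTCL from the non-Hodgkin lymphoma endpoint, the Annex 4 note includes it, and three of the four sites are sent to Annex 4 to identify cases

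*Protocol*

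**What the plan says.** Section 9.3.5 (Endpoints) gives the NHL definition twice. The endpoint list has "Non-Hodgkin lymphomas (excluding CTCL", closing the bracket there. The sentence on how lymphomas will be analysed by type has "cutaneous T-cell lymphoma, Hodgkin lymphoma, and non-Hodgkin lymphoma (excluding CTCL", again closing the bracket. CTCL is an endpoint in its own right.

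The note under Table A4-4 in Annex 4 states: "All the cutaneous lymphomas listed in Table A4-3 will also be counted toward the 'non-Hodgkin lymphoma' endpoint". It goes on to say that these codes also count toward any lymphoma, and that they were left out of Table A4-4 only to avoid listing them twice.

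Section 9.3.6 says where cases come from: "Potential cases of the targeted malignancies will be identified in PHARMO, Denmark, and Sweden using the list of ICD-O-3 codes shown in Annex 4". The abstract lists NHL as an endpoint without mentioning the CTCL exclusion. No text says whether section 9.3.5 or Annex 4 prevails.

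**The concern.** One endpoint under the primary objective has two incompatible definitions in current text. The annex note is not a passing remark on taxonomy. It names the endpoint and explains why the Table A4-3 codes are not repeated, which a programmer would take as an instruction to add them.

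Section 9.1 leaves room for sites to differ: "Each participating database research partner will adapt this core protocol to the specific needs of the local database". The coordinating centre receives stratified counts rather than individual records (section 9.7), so it could not easily reclassify cases afterwards.

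Three things are at stake:

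- whether the Extension NHL results can be set beside Phase I and Table 4;
- whether all four databases count the same events;
- whether bias particular to CTCL passes into a second endpoint. Section 9.3.6.1 plans a case-level check for protopathic bias for CTCL only, and in the CPRD and Sweden only.

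**Working it through.** **Step 1. Can the two texts be reconciled by reading the note narrowly?** The note would be harmless if Table A4-3 held something other than CTCL.

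- Table A4-3 lists only mature T-cell and NK-cell codes. Section 9.3.5 describes it as the selection of cutaneous lymphoma codes that matched the WHO 2008 classification.
- Section 9.3.6, in its CPRD paragraph, ties that selection to the endpoint: "CTCLs will be identified using the selected ICD-O-3 codes that matched the definition and codes of cutaneous lymphomas".
- The note cannot be meant for cutaneous B-cell lymphomas, because section 9.3.5 keeps them out of the group: "Therefore CBCLs (which occur considerably less frequently than CTCLs) will not be included within the cutaneous lymphomas group in this study".

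So the note adds the CTCL codes to NHL, and the texts conflict. The code-block headings do not help: the NHL block in Table A4-4 is headed 967-972, which spans the 970-971 block that heads Table A4-3.

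**Step 2. Which definition do the planning rates follow?** The inputs are the adult rates per 100,000 person-years in Table 4, which its footnote attributes to Phase I: NHL 18.1, Hodgkin 4.4, CTCL 3.1. The any-lymphoma row reads "Lymphoma 25.6 0.99", where the first number is the rate.

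- If NHL excludes CTCL, the three types add up to any lymphoma: 18.1 + 4.4 + 3.1 = 25.6. This matches exactly.
- If NHL includes CTCL, NHL and Hodgkin alone should add up: 18.1 + 4.4 = 22.5. This does not match.

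The adult planning rates therefore follow section 9.3.5.

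**Step 3. Size of the change under the annex note (adults).**

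- Rate: 18.1 + 3.1 = 21.2 per 100,000.
- Relative increase: 3.1 / 18.1 = 17.1%.
- CTCL share of the inclusive endpoint: 3.1 / 21.2 = 14.6%.
- Expected tacrolimus cases in the 551,369 adult person-years of Table 3, at these rates: 551,369 × 18.1 / 100,000 = 99.8 without CTCL, and 551,369 × 21.2 / 100,000 = 116.9 with it. The difference is 17.1 cases.

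**Step 4. Does precision change?** Take the probability that the upper 95% limit falls below 2 at a true rate ratio of 1 as Φ(ln 2 / √(1/e₁ + 1/e₀) − 1.96), with e₁ the exposed cases and e₀ = 4e₁. At the 198,400 Phase I adult person-years, e₁ = 35.9 gives 0.960 and e₁ = 42.1 gives 0.980. The difference is small. The issue is definition and bias, not precision.

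**Step 5. How far would CTCL-specific bias carry into NHL?** With comparator rates as in Table 4,

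NHL rate ratio = (18.1 × RR for NHL without CTCL + 3.1 × RR for CTCL) / 21.2.

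Set the true NHL ratio to 1.0. The CTCL ratios are assumptions; the protocol gives none for this comparison.

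| Assumed CTCL RR | Calculation | Resulting NHL RR |
|---|---|---|
| 1 | (18.1 + 3.1) / 21.2 | 1.00 |
| 2 | (18.1 + 6.2) / 21.2 | 1.15 |
| 3 | (18.1 + 9.3) / 21.2 | 1.29 |
| 5 | (18.1 + 15.5) / 21.2 | 1.58 |

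**The case against.** **Safeguards exist.** Section 9.7 says the Phase I analyses will be repeated except where indicated, and the Phase I adult rates already use the exclusive definition. A common statistical analysis plan, not at hand here, is to document all diagnostic codes. Section 9.1 makes the coordinating centre responsible for consistent variable definitions. The CPRD does not code neoplasms in ICD-O-3 and works from a mapping, so the direct instruction to use Annex 4 covers three sites, not four. All of this stands. It makes divergence a possibility rather than an expectation, but it does not remove the contradictory sentence.

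**The analysis offers partial protection.** CTCL is reported separately. Sensitivity analysis 5 in section 9.7.2.5 splits cutaneous from noncutaneous lymphoma, and sensitivity analysis 7 varies the lag up to 48 months beyond the standard 6. These would help to expose an excess driven by CTCL. They are partial, because the sensitivity analyses cover single use only and the noncutaneous group pools Hodgkin lymphoma with NHL.

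**A reader might infer a false NHL signal.** The documents do not show one.

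- Take 551,369 person-years, full 4:1 comparators and no stratification, so the comparator has 4 × 116.9 = 467.6 cases. At a CTCL ratio of 3 the exposed cases are 116.9 × 1.29 ≈ 151, the standard error is √(1/151 + 1/467.6) ≈ 0.094, and the 95% interval is about 1.08 to 1.55.
- At a CTCL ratio of 2 the exposed cases are about 134, the standard error is about 0.098, and the lower limit is 1.15 / 1.21 ≈ 0.95. Excluding 1 needs a CTCL ratio of roughly 2.4 or more.
- The tacrolimus ratios cited in section 7.1 for cutaneous or T-cell lymphoma (2.5 and 3.1) are against untreated patients or nonusers. Here the comparator is corticosteroid users. For them the same section cites ratios of 3.8 to 82.9 for lymphomas with skin involvement and offers misdiagnosed early lymphoma and confounding by indication as explanations. The comparator may share the bias, so the net effect could be small or go either way.
- Matching is up to 4:1, and section 9.9 bases interpretation on the point estimate, upper limit and absolute excess risk, not on whether the interval excludes 1.

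**A reader might also infer that NHL was meant to be free of protopathic bias.** No passage says so. Section 7.1 warns that noncutaneous lymphomas too may first produce skin symptoms. Section 9.3.5 leaves cutaneous B-cell lymphomas, and rare cutaneous lymphomas coded less specifically, within NHL.

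**Conclusion.** The protocol is wrong as written. Section 9.3.5 and the Annex 4 note define NHL differently, and no reading of Table A4-3 reconciles them. The adult sum in Table 4 shows that the Phase I planning rates exclude CTCL.

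The paediatric rates (0.5 + 1.6 = 2.1) look like a second proof but are not. Footnote b of Table 4 says there were no Phase I CTCL cases in children unexposed to tacrolimus and takes the 0.2 rate from an external source, so the sum is the same under either definition.

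Following the annex would raise the adult NHL rate by 17%, to 21.2 per 100,000, with 14.6% of events being CTCL. The result would not be comparable with Phase I or Table 4, and possibly not between sites. The carry-over of bias (NHL ratio 1.00 to 1.58 for assumed CTCL ratios of 1 to 5) is illustrative only. It requires both that a site follows the note and that CTCL carries a raised ratio against corticosteroid users. Any lymphoma, Hodgkin lymphoma and CTCL are the same under both texts.

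This is a genuine inconsistency in one endpoint that should be corrected, but it does not put the study as a whole in doubt.

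**What to change.** Rewrite the note under Table A4-4 so that Table A4-3 codes count toward CTCL and any lymphoma only, and the NHL endpoint uses only the individual non-Hodgkin codes listed in Table A4-4. Selecting by the 967-972 block heading would bring the CTCL codes back in. In the abstract's endpoint list, label the endpoint non-Hodgkin lymphoma (excluding CTCL). This restores the definition already in section 9.3.5 and reflected in the adult rates of Table 4.

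The cost is one sentence in the annex, one label in the abstract, and a check that each site's programming specification agrees. It is cheapest before extraction: once sites have submitted aggregated counts, any site that followed the note would have to regenerate its NHL tables.

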Annex 5.

List of Variables for the Estimation of Propensity Scores and Description of the Study Cohorts

Note: Additional variables to be included in the description of the study cohorts are detailed in section 9.7.1.1

Demographics and Lifestyle Habits

- Age
 - Children (years): 0-1, 2-4, 5-9, 10-14, 15-17
 - Adults (years): 18-24, 25-34, 35-44, 45-54, 55-64, 65-74, 75-84, 85+
- Sex
- Smoking history at the start date: current nonsmoker, current smoker, former smoker, unknown (CPRD)
- Body mass index at the start date: <20, 20-25, >25, unknown (CPRD)
- Socioeconomic status (PHARMO and CPRD)
- Calendar year of the start date: 2002, 2003, 2004, 2005, 2006, 2007, 2008, 2009, 2010, 2011, 2012, 2013, 2014 (additional years to be included if available)
- Primary care health practice/geographic region or outpatient pharmacy geographic region code (PHARMO)

Atopic Dermatitis

- Outpatient diagnosis of atopic dermatitis at any time before the start date
- Hospital discharge diagnosis of atopic dermatitis at any time before the start date
- Severe atopic dermatitis (yes/no):
Based on the use of health care resources in the year before the start date, severe atopic dermatitis is defined as any patient meeting any one of the following criteria [4,40,41]:
 - At least one visit to the dermatologist for patients aged younger than 3 years
 - At least four physician or pediatrician visits for atopic dermatitis in patients aged 3 years or older
 - At least one hospitalization with a primary discharge diagnosis for atopic dermatitis
- Type of prescriber of first prescription of study medications: dermatologist versus nondermatologist (PHARMO, Denmark, Sweden)

Medical History

Medical history ascertained by outpatient (GP, specialist, hospital outpatient) and/or hospital discharge diagnosis recorded at any time before the start date (yes/no).

Disease Classification	Individual Variables to be Evaluated (ICD-9)
Disease interacting with the immune system	Psoriasis (696)
	Epstein-Barr virus infection (075)
	Rheumatoid arthritis (714)
	Systemic lupus erythematosus (710.0)
	Sjögren's syndrome (710.2)
	Celiac sprue (579.0)
	Asthma (493)
	Allergic rhinitis (477)
	Diseases of the immune system (279)
Skin disease (excluding atopic dermatitis, eczema and psoriasis)	Inflammatory skin diseases (690, 691.0, 692.0-692.8, 693-695, 697, 698)
	Other skin diseases (700-709)
Chronic disease	Malignancy (140-171, 174-199, 203-208, 230-231, 232-238.1, 238.3-238.9) excluding skin cancer (172,173, 232, 238.2) and lymphoma (200-202)
	Renal failure (584)
	Chronic liver disease and hepatic failure (570, 571, 572.2, 572.3, 572.4, 573)
	Ischemic heart disease (410-414)
	Hypertensive disease (401-405)
	Heart failure (428)
	Other cardiovascular diseases (390-398, 415-417, 420, 427,429, 440-448)
	Cerebrovascular diseases (430-438)
	Diabetes mellitus (250)
	Chronic obstructive pulmonary disease (COPD), emphysema, respiratory insufficiency (491, 492, 496, 518.8)
	Musculoskeletal system and connective disease (excluding rheumatoid arthritis, systemic lupus erythematosus, and Sjögren's syndrome) (710.1, 710.3-710.9, 711-713, 715-739)
	Organ transplantation (V42, V43.2, 996.8)
	HIV infection or AIDS (042, V08)

Use of Medications

At least one prescription recorded within 1 year before the start date (yes/no, unless other parameters are specified)

Medication Category	Individual Variables To Be Evaluated (ATC code)
Use of immunosuppressant, immunostimulant and cytostatic drugs	Systemic corticosteroids (H02AB, H02B)
	Systemic tacrolimus (L04AD02)
	Azathioprine (L04AX01)
	Methotrexate (L01BA01, L04AX03)
	Ciclosporin (L04AD01)
	Other antineoplastic agents excluding methotrexate (L01 except L01BA01)
	Other immunosuppressants (L04AA, L04AB, L04AC, L04AD03, L04AX02, L04AX04, L04AX05, L04AX06)
	Immunostimulants (L03)
Antipsoriatics for topical use	Systemic antivirals (J05)
	Tars (D05AA)
	Antracene derivatives (D05AC) (dithranol and dithranol combinations)
	Psoralens for topical use (D05AD) (trioxsalen, methoxsalen)
Antipsoriatics for systemic use	Other antipsoriatics for topical use (D05AX) (fumaric acid, calcipotriol, calcitriol, tacalcitol, tazarotene, calcipotriol combinations)
	Psoralens for systemic use (D05BA) (trioxsalen, methoxsalen, bergapten)
	Retinoids (D05BB) (etretinate, acitretin)
Other dermatological preparations excluding topical corticosteroids	Other antipsoriatics (D05BX) (fumaric acid derivatives, combinations)
	Topical salicylic acid preparations (D02AF, D01AE12)
Other drugs	Other dermatological agents (D01-D04, D06, D08-D11)
	Cardiovascular system drugs (excluding lipid-modifying agents) (C01-C09)
	Anti-inflammatory and antirheumatic agents, nonsteroidal (M01A)
	Other antirheumatic agents (M01B, M01C)
	Hormone-replacement therapy (G03C, G03E, G03F)
	Lipid-modifying agents (C10)
	Insulins (A10A)
	Oral antidiabetics (A10B)
	Antiepileptics (N03)
	Drugs for asthma and obstructive airways disease excluding inhaled corticosteroids (R03A, R03BB, R03BC, R03BX, R03C, R03D)
Inhaled corticosteroids (R03BA)	

Utilization of Health Care Resources

Utilization of health care resources in the year before the start date.

Resource Category	Individual Variables to be Evaluated
Outpatient	Number of visits to general practitioner: 0, 1, 2-3, 4+
	Number of visits to dermatologist: 0, 1, 2-3, 4+
	Number of visits to pediatrician: 0, 1, 2-3, 4+
	Number of emergency department visits: 0, 1, 2-3, 4+
	Number of outpatient hospital visits: 0, 1, 2-3, 4+
Inpatient	Number of hospitalizations (excluding emergency department visits and hospital outpatient visits): 0, 1, 2-3, 4+
Prescriptions	Number of prescriptions: 0, 1, 2-4, 5-9, 10+

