We assumed that topical tacrolimus and topical pimecrolimus are prescribed only for atopic dermatitis and that members of these cohorts are not required to have a recorded diagnosis of atopic dermatitis. However, some patients may be prescribed these medications for skin disease other than atopic dermatitis. Bias from misclassification of atopic dermatitis among these patients could be present if the risk of skin malignancies associated with the underlying skin disease for which these medications are prescribed differs from the risk associated with atopic dermatitis. The magnitude of the bias would depend on the proportion of patients prescribed topical tacrolimus or topical pimecrolimus to treat skin disease other than atopic dermatitis. However, skin diseases that could be treated with these medications are infrequent, particularly in children, and may include inverse psoriasis (flexural psoriasis) and facial psoriasis [24]. For other skin diseases, such as vitiligo and alopecia areata, there seems to be limited effect of topical tacrolimus or pimecrolimus, and both diseases are slightly more common among children with atopic dermatitis [25,26]. Other disorders such as pyoderma gangrenosum, cutaneous lupus erythematosus, and oral lichen are even rarer in children [27-29]. Lichen sclerosus et atrophicus (LSA) is also uncommon in children [30]. LSA usually responds very well to treatment with very potent topical corticosteroids (clobetasol propionate), which reduces the need for topical tacrolimus or pimecrolimus [30]. Overall, these data indicate that the magnitude of a potential bias caused by misclassification of atopic dermatitis in users of topical tacrolimus and topical pimecrolimus will probably be low. To minimize potential bias, we will include in the estimation of propensity scores individual variables for specific skin diseases that potentially can be treated with topical tacrolimus or topical pimecrolimus. Several databases capture only partial information about the occurrence or severity of atopic dermatitis. During the JOELLE Extension, we plan to use type of prescribing physician (dermatologist or nondermatologist) as a proxy for severity of atopic dermatitis.

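### Section 9.9 relies on individual propensity-score variables for specific non-atopic skin diseases, but Annex 5 provides one for psoriasis only and pools the rest into two yes/no groups

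*Protocol*

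**What the plan says.** Section 9.9 accepts that some tacrolimus and pimecrolimus users are treated for skin disease other than atopic dermatitis. It says bias follows if that disease carries a different cancer risk. It argues that the bias is probably low because such use is infrequent, and adds a safeguard: "we will include in the estimation of propensity scores individual variables for specific skin diseases that potentially can be treated with topical tacrolimus" or pimecrolimus.

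The same paragraph names the diseases it has in mind:

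- Treatable conditions "may include inverse psoriasis (flexural psoriasis) and facial psoriasis".
- "For other skin diseases, such as vitiligo and alopecia areata, there seems to be limited effect of topical tacrolimus or pimecrolimus".
- "Other disorders such as pyoderma gangrenosum, cutaneous lupus erythematosus, and oral lichen are even rarer in children".
- "Lichen sclerosus et atrophicus (LSA) is also uncommon in children".

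Annex 5 lists the propensity-score variables. Psoriasis (696) has its own row, and the medication table adds topical and systemic antipsoriatics. Systemic lupus has a row; cutaneous lupus does not. Apart from the atopic dermatitis items, the remaining skin diagnoses form two rows: "Inflammatory skin diseases (690, 691.0, 692.0-692.8, 693-695, 697, 698") and "Other skin diseases (700-709"). Section 9.7.1.4 refers to Annex 5 for the covariates to be evaluated and selects among variables with a high-dimensional propensity-score algorithm.

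**The concern.** The safeguard in Section 9.9 works only if the score can tell the diseases apart. A yes/no variable covering many diagnoses balances how often any of them occurs, not their mix. If one disease in a group is commoner in one cohort and has its own skin-cancer or lymphoma risk, the matched and stratified comparison stays confounded by it.

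The planned diagnostics would not reveal this. Section 9.7.1.1 describes the cohorts with the Annex 5 variables plus a short list of extras, none of which is a non-atopic skin diagnosis. Section 9.7.1.4 compares patient characteristics before and after matching. A pooled row can look well balanced while its components are not. The study report could then repeat the claim of Section 9.9 although the covariate list supports it only for psoriasis.

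The rarity argument is also made mostly for children. By Table 3, adults are 98,788 of 98,788 + 24,412 = 123,200 expected tacrolimus users, about 80%.

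**Working it through.** **Side-by-side check.** The plan gives no figure to reproduce here, so the first step is a count.

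| Condition named in Section 9.9 | Own variable in Annex 5? |
|---|---|
| Psoriasis (inverse, facial) | Yes, as psoriasis (696), not split by site |
| Vitiligo | No |
| Alopecia areata | No |
| Pyoderma gangrenosum | No |
| Cutaneous lupus | No (systemic lupus only) |
| Oral lichen | No |
| Lichen sclerosus | No |

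One of seven has its own variable. The documents give no disease-to-code map, so whether all six others fall inside the two pooled rows cannot be confirmed.

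**Illustration of size.** The documents give no prevalence of these diseases by cohort and no disease-specific cancer risk. The prevalences and disease-outcome rate ratios (RR) below are therefore assumptions.

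Assume a disease in 5% of tacrolimus users and 0.3% of corticosteroid users, inside a group present in 30% and 20%. Balancing the group at 30% leaves the disease at p1 = 5% in the exposed and p0 = (0.3/20) × 30% = 0.45% in the comparator.

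Null rate ratio after balancing = [1 + p1(RR − 1)] / [1 + p0(RR − 1)]:

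- RR 0.5: 0.975/0.99775 = 0.977
- RR 1.5: 1.025/1.00225 = 1.023
- RR 2: 1.050/1.0045 = 1.045
- RR 3: 1.100/1.009 = 1.090

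With 2% versus 0.2% in the same group, p0 = (0.2/20) × 30% = 0.3%. The range is 0.990/0.9985 = 0.991 (RR 0.5) to 1.040/1.006 = 1.034 (RR 3).

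If the disease were concentrated in the corticosteroid cohort instead, with p1 and p0 exchanged, the ratios invert: 1.090 becomes 1/1.090 = 0.917.

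**Against precision.** Expected exposed cases are the person-years in Table 3 times the rate in Table 4. Assuming a full 4:1 ratio in person-time and equal rates, SE(log rate ratio) = √(1/a + 1/(4a)) = √(1.25/a), where a is the number of exposed cases. The last column is ln(1.090) = 0.086 divided by the SE.

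| Endpoint | Exposed cases | SE | Worst case above, in SE |
|---|---|---|---|
| Adult NMSC | 551,369 × 286.2/100,000 = 1,578 | 0.028 | 3.1 |
| Adult melanoma | 551,369 × 34.7/100,000 = 191 | 0.081 | 1.1 |
| Adult lymphoma | 551,369 × 25.6/100,000 = 141 | 0.094 | 0.9 |
| Adult CTCL | 551,369 × 3.1/100,000 = 17 | 0.27 | 0.3 |
| Pediatric lymphoma | 133,285 × 2.1/100,000 = 2.8 | 0.67 | 0.13 |

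For adult NMSC the 5% scenarios span 0.8 to 3.1 SE, and the 2% scenarios 0.3 to 1.2 SE.

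**The case against.** The strongest reply is that Section 9.9 commits to less than it seems to. It speaks of specific diseases, not of every non-atopic disease. The conditions it directly presents as treatable with the drugs are forms of psoriasis, which is well covered by its own row and the antipsoriatic variables. It doubts the drugs' effect in vitiligo and alopecia areata. It notes that lichen sclerosus responds well to very potent corticosteroids, which would push that disease towards the comparator. All of this stands, so a reader who infers that the promised control is absent altogether goes too far. It is present for psoriasis and coarse for the rest.

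A second reply is that the Annex 5 column heading calls every row an individual variable, and that Section 9.7 leaves code lists to the statistical analysis plan, which is not shown. The heading does not turn a row spanning ten three-digit codes into a variable for a specific disease. Code lists may properly be left to the analysis plan, but Annex 5 itself fixes the grouping, and the amendment table in Section 5 calls it the final list. The high-dimensional algorithm might bring in code-level covariates, but Section 9.7.1.4 does not say so.

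A third reply is sparsity. Section 9.2.3.3 reports very low recording even of atopic dermatitis outside the CPRD, and Section 9.9 says three sources rely on hospital diagnoses. Separate flags may often be nearly empty there. This stands, and the fix allows for it.

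Two stronger inferences should be resisted. One is that these diseases necessarily concentrate among tacrolimus or pimecrolimus users; no cohort-specific prevalence is given, and the lichen sclerosus remark suggests the opposite for that disease. The other is that the roughly 50% loss reported in Section 9.3.1 measures non-atopic use. That figure combines medication and diagnosis exclusions, and its leading examples are psoriasis and antipsoriatic drugs, which Annex 5 already enters separately.

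**Conclusion.** The inconsistency is real: Section 9.9 offers individual variables for specific skin diseases as its protection against confounding by non-atopic indication, and Annex 5 supplies one for psoriasis alone. For the other named diseases, adjustment is at best through pooled groups whose balance does not establish balance of their contents.

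The consequence is modest. Neither the size nor the direction of residual confounding can be derived from the documents. Under the assumed inputs, a null rate ratio shifts by about 10% at most, small beside the thresholds of 2, 4, 8 and 16 used in Table 4. It would matter mainly for adult NMSC, where precision is high enough for such a shift to show. In children and for rare lymphomas, sampling error dominates. These statements rest on the assumed prevalences and rate ratios and on a full 4:1 comparator, which the protocol gives only as an upper limit. The point is worth correcting because the stated bias control and the covariate list should agree, not because a large bias has been shown.

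**What to change.** In Annex 5, add separate yes/no variables for vitiligo, alopecia areata, pyoderma gangrenosum, cutaneous lupus, oral lichen and lichen sclerosus, and keep a residual group for other skin disease. Make them candidates for the propensity-score model wherever counts allow, pooling where they are too sparse, for example in children or in hospital-based sources. Report their balance before and after matching, including where they had to be pooled for modelling, if disclosure rules permit.

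Where separate variables are not feasible, reword Section 9.9 to say that only psoriasis is entered individually, that other skin diseases are grouped, and that residual confounding by indication from the grouped diseases remains possible.

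The cost is a few extra covariates based on diagnosis codes in the existing sources, some of them sparse or under-recorded. The rewording costs nothing.
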